Forty patients aged 5-20 years will be enrolled in the study. These subjects will be recruited from the pediatric pulmonary or pediatric sleep clinic at CCHMC. Patients who are suspected of having OSA will be referred in the usual manner to the sleep center for diagnostic sleep study (PSG). Following the establishment of OSAS diagnosis and subsequent enrollment in the study, the subject will begin therapy with APAP which will continue for 4 to 8 weeks. In that period of time the clinically ordered in-hospital CPAP titration study will be completed. The subject will then be randomized to either traditional fixed pressure CPAP at the pressure determined by in-hospital titration or APAP. The subject will receive 4 weeks of treatment in the randomized group (CPAP or APAP) then crossover to 4 weeks in the alternate group (CPAP or APAP). Both patient and researcher will be blinded to the randomization of pressure modality. The total study period will range from 14-18 weeks.

Appropriate statistical analyses will be used to evaluate two primary outcomes which are (1) the optimal pressure derived from APAP versus CPAP titration study and (2) the adherence to APAP versus fixed pressure CPAP. Other secondary outcomes will be compared between APAP and fixed pressure CPAP including the change in the score of Michigan Pediatric Sleep Questionnaire, Epworth Sleepiness Scale, Pediatric Quality of Life Inventory and CPAP Follow up Questionnaire.

2. PURPOSE OF THE STUDY:

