Forty-five subjects will be enrolled in the study, allowing for a 15% drop-out rate. When the total sample size is 40, the study design will have greater than 80% power to detect a difference in means of 1.000 (from published data, the difference between an APAP 90th pressure percentile of 10.4, SD = 1.4 and a mean CPAP titration of 9.4, SD = 1.9)⁵. In the crossover portion of the study, when the sample size in each sequence group is 20 (total sample size of 40), a 2 x 2 crossover design will have 80% power to detect a difference in means of 35.000 (from published data, the difference between an APAP mean minutes of use of 306, SD = 114 and a CPAP mean minutes of use of 271, SD = 115)⁶ using a two group t-test (Crossover ANOVA) with a 0.05 two-sided significance level.

B. Inclusion criteria

Patients aged 5 to 20 years, male or female, of any race and any socioeconomic background with moderate OSA defined as an AHI of ≥ 5 or obstructive hypoventilation, determined by a measured end tidal carbon dioxide level >50 for more than 25% of total sleep time will be included.

Exclusion criteria

Those patients with significant cranio-facial abnormalities, chromosomal abnormalities that would affect compliance, cerebral palsy, significant neurological disease or neuromuscular disease will be excluded from the study.

C. Recruitment

Patients seen by pulmonary or sleep providers in the CCHMC pulmonary or sleep clinics who are suspected of having OSA based on history and physical exam will be referred in the usual manner to the sleep center for a diagnostic sleep study. Those patients who meet inclusion criteria will be referred by their provider for enrollment in the study. Standard practice is for the patient to return to sleep clinic approximately 2 weeks after diagnostic PSG for follow-up and to discuss treatment options. Patients will be recruited for enrollment during that clinic visit.

D. Vulnerable populations

Subjects younger than 18 years old are considered vulnerable to coercion or undue influence and additional safeguards will be used to protect that population. Assent will be obtained after age-appropriate explanation of the study. The child will only participate voluntarily and will have the opportunity to withdraw at any time for any reason, independent of their parent or guardian. Assent will be reaffirmed before study procedures are performed.

7. PROCESS OF OBTAINING CONSENT:

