Once the patient has been enrolled in the study at the time of the first clinic visit following diagnostic PSG, the subject and/or parent will complete the Michigan Pediatric Sleep Questionnaire (PSQ), Pediatric Quality of Life Inventory (PedsQL) and Epworth Sleepiness Scale (ESS). This is standard practice for all patients seen in sleep clinic at each visit. The enrolled subject will be fitted with an appropriate CPAP interface (mask apparatus) by an experienced sleep technologist, and will be trained on use of the Resironics REMstar Auto device which will be set to APAP. The subject will continue to use the device at home every night for 4 to 8 weeks. During that period of time the subject will return for an in-hospital CPAP titration study. The CPAP titration study is the current standard of care for those diagnosed with OSAS and for whom treatment with CPAP is prescribed. Following CPAP titration the subject will return to clinic, a standard practice to initiate CPAP therapy. At that visit, device data from the treatment period will be downloaded including therapy usage hours, average 90th pressure percentile and average CPAP pressure. The PSQ, PedsQL and ESS will be re-administered, per current clinical practice. He or she will also complete a CPAP Follow-Up Questionnaire (CFQ) to score the comfort and side-effects of treatment. Questions similar to those found in the CFQ are typically reviewed with the patient during the regular clinic visit, however, for the purposes of the study, we will standardize those questions. The subject will then be randomized in a double blind fashion to either traditional fixed pressure CPAP at the pressure determined by in-hospital titration or APAP. This treatment will continue for 4 weeks, after which time the subject will return to clinic (standard follow-up after initiating CPAP therapy), where the PSQ, PedsQL, ESS and CFQ will be re-administered and data from the device will be downloaded. Treatment will continue for another 4 weeks on the alternative setting with the same device and same mask interface. The subject will present for follow-up sleep clinic appointment at the end of the second randomization period, at which time he or she will complete another PSQ, PedsQL, ESS and CFQ. Information from the device will be downloaded, and the study will end. This final clinic visit will occur approximately 1 month sooner than the typical follow-up appointment, but in all, the patient will not have additional visits beyond the standard clinical practice.

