For each patient, 90th APAP pressure percentile, average CPAP pressure delivered and therapy usage hours will be downloaded from the APAP device and recorded in a central database which will be stored on secure CCHMC servers. Questionnaire responses and CPAP titration values for each patient will be stored in like manner. Based on the study's outcome variables we anticipate requiring enrollment of 45 patients to power the study adequately, and to have enough subjects of each race, gender and pre-and post-adolescent ages. For analysis of the primary outcome of APAP run-in period vs. CPAP titration pressure, statistical analysis of the data will be completed using the standard 2 tailed paired t-test or Wilcoxon Signed-Rank test. To determine the effect of treatment on adherence and quality of life outcomes as well as any carry over effect in the crossover portion of the study, an appropriate mixed effects model including period, sequence, and subject effects will be employed¹¹.

10. FACILITIES and PERFORMANCE SITES:

All research activities will take place at CCHMC facilities including the CCHMC Pulmonary Sleep Center (sleep lab), pulmonary sleep clinic on Main campus, and pulmonary sleep clinic on Liberty Campus.

11. POTENTIAL BENEFITS:

Potential benefits to the patient enrolled in the study include the ability to receive prompt treatment for sleep disordered breathing once his or her diagnostic sleep study is read, instead of awaiting results from a subsequent CPAP titration study, as is the current practice. Subjects would benefit from the ability to use a machine that is potentially more comfortable than fixed CPAP, with potential for better

adherence to therapy, translating to improved resolution of symptoms and improved quality of life. Future patients may derive similar benefits from these study findings.

12. POTENTIAL RISKS, DISCOMFORTS, INCONVENIENCES AND PRECAUTIONS:

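### Enrolling 45 allows for 11% drop-out, not the stated 15%, around the 40 subjects used for power, and the abstract gives a different enrolment number (40)

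*Combined protocol and SAP*

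**What the plan says.** Section 6.A (Number of participants) sets enrolment and its allowance in one sentence: "Forty-five subjects will be enrolled in the study, allowing for a 15% drop-out rate". The two power statements that follow both use 40. For the pressure outcome: "When the total sample size is 40, the study design will have greater than 80% power to detect a difference in means of 1.000". For the crossover comparison of adherence, 80% power is claimed for a 35-minute difference "when the sample size in each sequence group is 20 (total sample size of 40"), with a two-sided 0.05 test.

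Section 9 (Data analysis/methods) repeats the larger number: "we anticipate requiring enrollment of 45 patients to power the study adequately". Section 1 (Abstract) has a different one: "Forty patients aged 5-20 years will be enrolled in the study".

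No section names an evaluable number other than 40, explains how 40 and 45 relate, or provides for replacing subjects who drop out.

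**The concern.** A drop-out allowance links the number enrolled to the number the power calculation needs. Here the three stated figures (45 enrolled, 15% lost, 40 for power) cannot all be true. If drop-out reaches the planned 15%, the crossover comparison has about two fewer completers than its design size. Its power is stated as 80% at 40, so there is no margin to absorb the loss. Adherence is one of the two primary outcomes. It needs data from two 4-week randomised periods after a 4 to 8 week run-in, so it bears all of the attrition.

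The second problem is the recruitment target. The abstract and section 6.A both describe their number as the number enrolled, so a reader of the abstract alone would stop recruiting at 40, which is the number the power calculation needs after losses.

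**Working it through.** **Inputs.** Enrolment 45 (sections 6.A and 9) or 40 (abstract); drop-out 15% (6.A); number used for power 40, as 20 per sequence (6.A); crossover difference 306 − 271 = 35 minutes, SDs 114 and 115, two-sided 0.05 (6.A); pressure difference 1.0, SDs 1.4 and 1.9 (6.A). The protocol gives no within-subject correlation for either outcome.

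**Trying to reproduce 45.**
- Correct inflation, N/(1 − d): 40/0.85 = 47.06, so 48 (47 × 0.85 = 39.95; 48 × 0.85 = 40.8).
- The common mistaken form, N × (1 + d): 40 × 1.15 = 46.
- Neither gives 45.

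**What 45 provides.**
- Largest drop-out that keeps 40: 1 − 40/45 = 5/45 = 11.1%.
- Expected completers at 15%: 45 × 0.85 = 38.25, about 38, or 19 per sequence if losses are balanced.
- If the abstract's 40 were the enrolment: 40 × 0.85 = 34.

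**Effect on crossover power.** Noncentral t with n − 2 degrees of freedom and noncentrality 35/(SD_d/√n), where SD_d is the SD of within-subject differences. SD_d is not stated, so I solved for the value that gives exactly 80% at n = 40. This is 77.0 minutes, which implies a correlation of (114² + 115² − 77.0²)/(2 × 114 × 115) = 0.77.

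| Assumed power at 40 | SD_d (min) | Power at 38 | Power at 34 |
|---|---|---|---|
| 79.5% | 77.5 | 77.3% | 72.4% |
| 80.0% | 77.0 | 77.8% | 72.9% |
| 80.5% | 76.5 | 78.4% | 73.5% |

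The outer rows cover only the possibility that the stated 80% is a rounded figure. At other correlations the level of power changes far more than the loss does:

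| Correlation | Power at 40 | Power at 38 |
|---|---|---|
| 0.5 | 47.0% | 45.0% |
| 0.7 | 68.2% | 65.8% |
| 0.8 | 84.6% | 82.6% |

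**Pressure outcome.** Paired t-test, SD_d = √(1.4² + 1.9² − 2ρ × 1.4 × 1.9). At n = 38, power is 80% at ρ = 0.184, 85.3% at ρ = 0.3 and 94.0% at ρ = 0.5. This is already the unfavourable case in which all 15% are lost before titration. Section 8 has these data collected at the clinic visit after titration and before randomisation ("device data from the treatment period will be downloaded including therapy usage hours, average 90th pressure percentile and average CPAP pressure"), and section 9 compares the run-in with the titration pressure ("For analysis of the primary outcome of APAP run-in period vs. CPAP titration pressure"). Subjects lost during the later 8 weeks therefore still count.

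**The case against.** The strongest reply is that very little turns on this. Two subjects cost about two percentage points of crossover power at each correlation tried, while the unstated correlation moves power from about 47% (at 0.5) to about 85% (at 0.8). That is true, and it is why the power figures here are conditional. It does not make the 15% statement correct.

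Several narrower points also carry some weight:

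- **Margin or forecast.** "allowing for a 15% drop-out rate" can be read as a planning margin. The shortfall arises only if drop-out exceeds 11.1%, so it should be put as what happens at 15%. Even read as a margin, 45 does not provide it.
- **The abstract's 40.** Both detailed sections say 45, and 40 equals the number used for power, so the abstract probably means evaluable subjects. The 34-subject case is therefore a consequence of taking the abstract literally, not the likeliest outcome. The abstract is nevertheless worded as enrolment.
- **Mixed model.** Section 9 plans a mixed effects model. If subject is a random effect, which is not stated, a participant lost after the first period still contributes some information, though little when the correlation is high. The power statement, however, rests on 20 per sequence in a two-group crossover t-test, and the allowance exists to protect that number.
- **47 or 48.** Rounding 39.95 to 40 makes 47 defensible. Neither number is 45.

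**Conclusion.** The concern holds. On the protocol's own figures, 45 enrolled allows for 11.1% drop-out around 40, not 15%, and 15% leaves about 38. The abstract's enrolment of 40 conflicts with the 45 in sections 6.A and 9. These conclusions use only printed numbers and need no assumption.

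The consequence for power is small and conditional. Crossover power is about 78% at 38 if it is exactly 80% at 40. It is about 73% at 34, which applies only if 40 is the true enrolment target and the same 15% is lost. Both figures depend on the back-solved SD of differences of about 77 minutes and on counting only subjects who complete both periods. No loss of adequate power is claimed for the pressure outcome: even with 38 subjects it keeps at least 80% for a correlation of about 0.18 or more.

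**What to change.** State one enrolment number throughout. The simplest choice is 45, with the abstract either corrected to 45 or its 40 labelled as the evaluable number. Then restate in section 6.A what 45 provides, in one of two ways:

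- 45 enrolled allows for 11% drop-out and keeps 40; or
- 45 enrolled leaves about 38 crossover completers at 15% drop-out, with crossover power of about 78% if it is exactly 80% at 40.

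With the second wording, state the SD of within-subject differences that the power rests on. Under either wording, give the expected number for the run-in pressure comparison separately, because it loses fewer subjects.

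The cost is two sentences and a slightly less favourable statement: 11% in place of 15%, or about 78% in place of 80%. If the sponsor prefers to keep both the 15% allowance and 40 completers, enrolment becomes 48. That means three more subjects within the 12-month enrolment window, and correcting the error does not require it.
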